15.2.3.9. Probabilistic Reward Task

Each outcome measure of the PRT will be summarized (mean, standard deviation, median, and range) at each visit. Response bias and discriminability will be summarized by block and treatment. Reaction time and hit rates will be summarized by stimulus (rich vs. lean), block and treatment. Line plots of means (+/-SD) will also be presented by treatment group and visit.

At each scheduled visit, an ANOVA model will be used to compare treatment groups. The models for response bias and discriminability will include terms for treatment, block, and treatment-by-block will be used to analyze treatment differences. The models for reaction time and hit rates will include terms for treatment, block, stimulus, and treatment-by-block will be used to analyze treatment differences. The models LS Means and standard errors (SEs) will be presented for each treatment group. The difference in LS Means with corresponding SEs, 95% confidence intervals for differences, and p-values will also be presented. No adjustments will be made for multiple comparisons.

All data, including the overall total scores, will be listed by treatment and patient.

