8. Proportion of patients who demonstrate significant clinical improvement, where **improvement** is defined by a score of 1 (very much improved) or 2 (much improved) on the CGI-I at Week 8.

The following secondary efficacy endpoints based on the performance tasks will be analyzed and presented in summary and graphical displays.

Data for the FERT will be summarized (mean, standard deviation, range) for each treatment group at each visit. All treatment differences will be estimated with 95% CI. No adjustments will be made for multiple comparisons. The analysis will employ ANOVA models without adjusting for covariates. However, if significant confounds are identified, a secondary analysis will be performed to examine the relationship between FERT outcome measures and other covariates. A full description of the statistical analysis methods for FERT outcome measures will be provided in in the SAP.

9. Outcome measures from the FERT
  - a) Accuracy
  - b) Misclassification
  - c) Average reaction time
  - d) Target sensitivity
  - e) Response bias

Data for all PRT outcome measures will be summarized (mean, standard deviation, range) for each treatment group at each visit. The ANOVA models will be used to compare between treatment groups. For “Response bias” and “Discriminability,” treatment group, block, and treatment-by-block interactions will be considered fixed effects. For “Reaction time” and “Hit rates,” the stimulus type will be included as an additional fixed effect. The details of the analysis methods for these outcome measures will be described in the SAP.

10. Outcome measures from the PRT

- a) Response bias
- b) Discriminability
- c) Reaction time
- d) Hit rates

Data for all EEfRT outcome measures will be summarized (mean, standard deviation, range) for each treatment group at each visit. Statistical analyses of the Preference during the EEfRT trial will be performed using Generalized Estimating Equation (GEE) models. A binary logistic distribution will be used to model the probability of the Preference. The relationship and interactions between Preference and independent variables of reward magnitude, reward probability, expected value, age, sex, and efficacy parameters will be explored. The ANOVA model will be used to compare the completion rates between treatment groups. The details of the analysis method for these outcome measures will be described in the SAP.

11. Outcome measures from the EEfRT

- a) Preference (hard or easy task choice)

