#### 15.2.1.9. Probabilistic Reward Task

The PRT is a measure of reward learning consisting of trials in which patients are asked to respond to two hardly distinguishable cues, of which one is more frequently rewarded. Patients complete a total 300 trials in 3 blocks of 100. Response bias for the rewarded category is the main outcome of interest (Pizzagalli, et al, 2008). In addition, the following outcome measures will be provided:

- Discriminability (subject's ability to differentiate between the two cues)
- Reaction time
- Accuracy (hit rates)

All measures will be computed and provided by the vendor in the source data for each block and as an overall total. The response bias and discriminability measures will also have log-linear adjusted values provided. The adjusted values for response bias and discriminability and original values for reaction time and hit rates at each block will be utilized in the analyses.

Additionally, there will be a series of checks on the data to insure validity of the data used in the analysis. Only subjects with data meeting the following criteria will be used in the analysis.

- The number of valid trials is >80% for each block
- Reward ratio of rich:lean is greater than 25:10 (ratio: 2.5) in each block.
- The number of rich rewards is between 24 and 30, inclusively.
- The number of lean rewards is between 7 and 10, inclusively.
- The lean accuracy in each block is greater than or equal to 40%.
- The rich accuracy in each block is greater than or equal to 40%.
- For combination of blocks e.g. Main, Total: If one block is not usable, then the combo is not usable (i.e. if block 2 is not usable, then total is not usable).

---

Document:	C:\Users\q718413\Documents\NEP-MDD-201_SAP_v1.0_Final_06Dec2018.docx		
Author:	[name]	Version Number:	1.0
		Version Date:	06Dec2018

Template No: CS\_TP\_BS016 Revision 4  
Effective Date: 01Apr2016

Reference: CS\_WI\_BS005

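### The PRT ANOVAs use 3 or 6 values per patient but specify no patient-level error term, so the treatment p-value and 95% CI are not valid in general

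*SAP*

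**What the plan says.** SAP 15.2.1.9 describes the task: "Patients complete a total 300 trials in 3 blocks of 100". The vendor supplies every measure by block and in total. For two of the measures, "The response bias and discriminability measures will also have log-linear adjusted values provided", and the block-level adjusted values are analysed. For the other two, "original values for reaction time and hit rates at each block will be utilized in the analyses".

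SAP 15.2.3.9 then fits one ANOVA per scheduled visit. For the first pair of outcomes: "The models for response bias and discriminability will include terms for treatment, block, and treatment-by-block will be used to analyze treatment differences". For the second pair, which are split by rich and lean stimulus: "The models for reaction time and hit rates will include terms for treatment, block, stimulus, and treatment-by-block". LS means, their differences, SEs, 95% CIs and p-values are to be reported.

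Protocol 13.2.8.3 agrees: "treatment group, block, and treatment-by-block interactions will be considered fixed effects", and for reaction time and hit rates "the stimulus type will be included as an additional fixed effect". It leaves the details to the SAP. Neither document adds a patient effect, a repeated-measures statement or a covariance structure for the PRT.

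Other repeated data in the SAP are given a method. The primary MADRS model has an unstructured within-patient covariance (15.1.3), and EEfRT preference uses GEE (15.2.3.10).

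**The concern.** Randomization assigns treatment to patients, so the treatment difference should be judged against variation between patients. The listed model judges it against the pooled residual of 3 or 6 values per patient, as if each were a separate person. Values from one patient at one sitting cannot be assumed independent, and the SAP gives no reason to do so. Where they are positively correlated on balance, the SE of the treatment difference is too small.

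PRT performance is a named secondary objective, and response bias is its main outcome. SAP 6.5 calls p<0.10 a trend and p<0.05 a strong trend. A treatment difference could therefore earn either label more often than its nominal rate, with a CI narrower than it should be. The PRT subgroup analysis by SHAPS (≤7, >7) in SAP 15.3.4 reuses the method and so has the same missing error term.

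**Working it through.** **Inputs from the documents.** There are 3 blocks (SAP 15.2.1.9) and 2 stimuli for reaction time and hit rates (SAP 15.2.3.9), so m = 3 or m = 6 values per patient and visit. Tests are two-sided at 10% (Protocol 13.2.8.3). The documents state no PRT power, variance or correlation. For simulation I use 44 per arm, taken from the MADRS calculation in Protocol 13.1. That calculation reproduces: effect size 0.5 and two-sided alpha 0.10 give 75.2% power (noncentral t) against the stated 75%.

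**Assumed.** Equal variances and a common within-patient correlation r, shown as a range.

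**Formulas.** With m values per patient, the true variance of the treatment contrast is that of the listed ANOVA times F = 1 + (m − 1)r. The true level of the nominal 10% test is 2Φ(−1.645/√F), and of the nominal 5% test 2Φ(−1.960/√F). The true coverage of the 95% CI is one minus the latter. Example: m = 3 and r = 0.3 give F = 1.6, 1.645/1.265 = 1.300 and a level of 19%.

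| m | r | F | Level at nominal 10% | Level at nominal 5% | Coverage of 95% CI |
|---|---|---|---|---|---|
| 3 | −0.1 | 0.8 | 6.6% | 2.8% | 97% |
| 3 | 0 | 1.0 | 10% | 5% | 95% |
| 3 | 0.1 | 1.2 | 13% | 7.4% | 93% |
| 3 | 0.3 | 1.6 | 19% | 12% | 88% |
| 3 | 0.5 | 2.0 | 24.5% | 17% | 83% |
| 3 | 0.7 | 2.4 | 29% | 21% | 79% |
| 6 | 0.1 | 1.5 | 18% | 11% | 89% |
| 6 | 0.3 | 2.5 | 30% | 22% | 78% |
| 6 | 0.5 | 3.5 | 38% | 29% | 71% |
| 6 | 0.7 | 4.5 | 44% | 36% | 64% |

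**Simulation of the listed ANOVA** (44 per arm, 8,000 trials per cell, nominal 10%). At r = 0/0.3/0.5/0.7 the level is 10.0/19.6/24.5/28.2% for m = 3 and 9.9/28.8/37.4/44.1% for m = 6. A t-test on one mean per patient holds 9.1 to 10.4% in every cell.

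**Mixed signs, m = 6.** Rich and lean hit rates may move in opposite directions. Let a be the rich-lean correlation within a block, b the same-stimulus correlation across blocks, and c the rich-lean correlation across blocks. Then F = 1 + a + 2b + 2c.
- (a, b, c) = (−0.2, 0.5, −0.2): F = 1.4, level 16%.
- (−0.2, 0.3, −0.2): F = 1.0, level 10%.
- (−0.3, 0.3, −0.3): F = 0.7, level 5%.

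**Subgroup analysis.** SAP 15.3.4 analyses change from baseline to week 8, so stable differences between patients cancel. Split the variance of a block value into stable, visit-specific and residual parts. The between-block correlation of change scores is then visit/(visit + residual). Three assumed splits, each with a single-visit correlation of 0.5 (level 24.5%) and m = 3:
- 0.5/0/0.5: change-score r = 0, level 10%.
- 0.4/0.1/0.5: r = 0.17, level 15%.
- 0.25/0.25/0.5: r = 0.33, level 20%.

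**The case against.** The strongest reply is that a repeated-measures ANOVA was intended and that listing only fixed effects is shorthand. The table shells are not part of the text and might show it. But no wording says so, and the SAP does name a method for repeated values elsewhere. A programmer following 15.2.3.9 literally would fit independent errors.

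The second reply is that the size is unknown. That stands. A reader might infer from the table that the PRT results are bound to be inflated two- to fourfold. The documents do not support this: they give no correlation, and for hit rates the average may be near zero or negative.

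A reader might also infer that the SHAPS subgroup analysis is inflated by the same amount. For a fixed correlation group size hardly matters (m = 3, 22 per arm, r = 0.1/0.3/0.5/0.7: 13.5/18.8/24.2/28.4%). But the subgroup analysis is of change scores, whose correlation may be lower, so the same inflation cannot be claimed.

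Treatment-by-block and single-block tests would also have wrong error terms in general, in either direction. SAP 15.2.3.9 does not clearly promise p-values for them, so the point rests on the treatment difference alone.

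Finally, PRT p-values are nominal and unadjusted, and no decision rule uses them. That limits the severity, but a nominal p-value must still be valid for its own test.

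**Conclusion.** The point holds. As listed, the PRT models use the wrong error term for treatment, and the reported p-values and 95% CIs are valid only if a patient's values happen to be uncorrelated on balance. With positive average correlation the nominal 10% test runs at 13 to 29% (3 values) or 18 to 44% (6 equally correlated values) for assumed r from 0.1 to 0.7. With zero or negative average correlation the excess disappears or the test becomes conservative. These sizes assume equal variances and balanced data. The data validity checks in SAP 15.2.1.9 may reduce the numbers and make the formula approximate.

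The subgroup analysis shares the omission, with inflation that may be smaller. The primary MADRS analysis is untouched. This should be fixed, but it does not threaten the trial's main conclusion.

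**What to change.** Before unblinding, amend SAP 15.2.3.9 so that the overall treatment contrast is tested with the patient as the error unit.

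1. **Simplest.** Take one value per patient and visit, the equal-weight mean of the analysed block (and stimulus) values, and compare it between arms. For response bias and discriminability this is the mean of the log-linear adjusted values. Do not substitute the vendor total, since nothing in the documents shows that it equals this mean.
2. **If block-level output is wanted.** Use a mixed model with the same fixed effects, a stated within-patient covariance and a small-sample degrees-of-freedom correction such as Kenward-Roger. Use an unstructured covariance over the 3 blocks. For 6 values, use a block-by-stimulus structure that allows a negative rich-lean correlation, with a stated fallback, because an unstructured 6×6 matrix has 21 parameters.

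The correction in option 2 is needed. An unstructured 6×6 model with t on 2n − 2 degrees of freedom (assumed a = 0.3, b = 0.3, c = 0.2) ran at 11.5/13.3/13.9% with 44/22/15 per arm in 2,000 simulated trials.

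For the 6-value outcomes, state that the estimand is the equal-weight average over stimuli, and add treatment-by-stimulus if the mixed model is used. Without that term the covariance sets the weights. With the same correlations, lean SD 1.5 times rich SD, and a true effect of 1 on rich and 0 on lean, the model estimates 0.82 where the patient mean gives 0.50.

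Apply the same wording to the change-from-baseline PRT subgroup analysis.

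**Cost.** SAP text and a change of SAS procedure; the vendor already supplies block values. CIs will usually widen to their correct width. Under option 1 a patient with an unusable block may have no value. The SAP already takes that approach for combined scores: "If one block is not usable, then the combo is not usable".

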## 9.2 VISIT 2: BASELINE (DAY 1)

The following order of procedures is recommended to prioritize eligibility and safety and assessments:

1. The Investigator will conduct/administer the following assessments (\*or his/her designee where asterisked):
  - a. Weight\*
  - b. Investigator-administered MADRS followed by the computer-administered MADRS
  - c. Allow patient to complete Hospital Anxiety and Depression Scale (HADS), Snaith-Hamilton Pleasure Scale (SHAPS), Dimensional Anhedonia Rating Scale (DARS), and pain question; reviewed by site personnel qualified to oversee completeness\*
  - d. Hamilton Anxiety Rating Scale (HAM-A)
  - e. C-SSRS
  - f. CGI-S and CGI-I
  - g. SHSF and if applicable, SHFU
  - h. Concomitant therapies review\*
  - i. Adverse events review
  - j. Neurological examination
  - k. Vital signs (BP and pulse both supine and standing, respiratory rate, temperature)\*

1. 12-lead ECG\*
- m. Urine drug screen and urine pregnancy test for women of child-bearing potential\*

The Investigator will confirm the patient's eligibility prior to completing the remaining randomization visit procedures. The following order of these procedures is recommended:

2. Complete randomization via IWRS
3. The rater will administer the FERT (Note the FERT must not immediately precede or follow the EEfRT or PRT)
4. Blood and urine collection for central laboratory analysis. Note: blood and urine may be collected earlier in the visit as long as it precedes administration of the FERT by > 1 hour.
5. The rater will administer the Probabilistic Reward Task (PRT) and Effort Expenditure for Reward Task (EEfRT) in the order assigned by IWRS
6. Collect and/or monitor digital assessments, as applicable
7. After completing all study procedures, the patient will take their first dose of investigational study drug (**one capsule**) with a light snack at the site from the bottle dispensed at this visit
8. Collect two blood samples for pharmacokinetic analysis (one between 15 min and 2 hours after dosing and another between 4 and 8 hours after dosing)
9. Dispense allocated study drug and instruct patient on the importance of compliance and returning the dispensed bottle with any unused study drug at each visit.
10. Instruct all patients to **take one capsule of their assigned study drug daily and not take study drug the day of their next visit.**

The Investigator will review the results of the central laboratory tests for safety prior to the next visit.

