#### 9.5 VISIT 5, WEEK 4 (DAY 29)

The following order of procedures is recommended to prioritize safety and efficacy assessments:

1. The Investigator will conduct/administer the following assessments (\*or by his/her designee where asterisked):
  - a. Weight\*
  - b. Investigator-administered MADRS followed by the computer-administered MADRS
  - c. Allow patient to complete HADS, SHAPS, DARS, and pain question; reviewed by site personnel qualified to oversee completeness\*
  - d. HAM-A
  - e. C-SSRS
  - f. CGI-I
  - g. SHSF and if applicable, SHFU
  - h. Concomitant therapies review\*
  - i. Adverse events review
  - j. Neurological examination
  - k. Vital signs (BP and pulse both supine and standing, respiratory rate,

temperature)\*

1. 12-lead ECG\*
2. Blood and urine collection for central laboratory analysis (including urine pregnancy test for women of child-bearing potential)
3. The patient-returned investigational study drug will be accounted for and patient will be re-instructed if found to be out of compliance
4. Complete IWRS
5. The rater will administer the PRT and EEfRT in the order assigned by IWRS
6. Collect and/or monitor digital assessments, as applicable
7. Collect three blood samples for pharmacokinetic analysis at the following time points: (1) prior to dosing, (2) between 15 min and 2 hours after dosing, and (3) between 4 and 8 hours after dosing
8. After completing all study procedures including the pre-dose pharmacokinetic blood sample, the patient will take their dose of investigational study drug from the bottle dispensed at this visit with a light snack at the site
9. Dispense allocated study drug and instruct patient on the importance of compliance and returning the dispensed bottle(s) with any unused study drug at each visit.
10. Instruct all patients to take their assigned study drug dose daily, **and not take study drug the day of their next clinic visit.**

The Investigator will review the results of the central laboratory tests for safety prior to the next visit.

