### 2.2. SECONDARY OBJECTIVES

The secondary objectives are as follows.

- To evaluate the effects of BTRX-246040 on anhedonia in adult patients with MDD.
- To evaluate the safety and tolerability of BTRX-246040 in adult patients with MDD.
- To evaluate the effects of BTRX-246040 on the performance of tasks as measured by the Facial Expression Recognition Task (FERT), Probabilistic Reward Task (PRT), and Effort Expenditure for Reward Task (EEfRT) in adult patients with MDD.

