15.2.3.8. The Facial Expression Recognition Task

For each emotion of the FERT, each outcome measure will be summarized (mean, standard deviation, median, and range) by treatment group at each visit. Line plots of means (+/-SD) will also be presented by treatment group and visit. Additionally, accuracy will be summarized by intensity level for each emotion and plotted versus intensity level in scatterplots.

At each scheduled visit, an ANOVA model with a term for treatment will be used to analyze treatment differences. LS Means and standard errors (SEs) will be presented for each treatment group. A second ANOVA model will be fit with additional factors of gender, baseline MADRS total score, and baseline FERT outcome measure. The difference in LS Means with corresponding SEs, 95% confidence intervals for differences, and p-values will also be presented. No adjustments will be made for multiple comparisons.

All data, including the accuracy response for each intensity level, will be listed by treatment and patient.

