15.2.3.10. Effort Expenditure for Reward Task

Each outcome measure of the EEfRT will be summarized (mean, standard deviation, median, and

---

Document:	C:\Users\q718413\Documents\NEP-MDD-201_SAP_v1.0_Final_06Dec2018.docx		
Author:	[name]	Version Number:	1.0
		Version Date:	06Dec2018

Template No: CS\_TP\_BS016 Revision 4  
Effective Date: 01Apr2016

Reference: CS\_WI\_BS005

Analysis Plan

---

range) by treatment group at each visit. Line plots of means (+/-SD) will also be presented by treatment group and visit.

The analysis of completion rates will use an ANOVA model with a term for treatment to analyze treatment differences at each scheduled visit. The models LS Means and standard errors (SEs) will be presented for each treatment group. The difference in LS Means with corresponding SEs, 95% confidence intervals for differences, and p-values will also be presented. No adjustments will be made for multiple comparisons.

The analysis of preference will be completed utilizing Generalized Estimating Equation (GEE) models. A binary logistic distribution will be used to model the dichotomous outcome of preference at each scheduled visit. At each visit a series of models using a variety of factors will be fit. All models in the series will include explanatory variables reward magnitude, reward probability, and expected value (reward magnitude X probability) as a base. For each series, four models will be fit. The first will include the base variables with the additional variable of interest with no interactions. The next three models will include the same but with an interaction term between the variable of interest and each base variable in order. The variables of interest that will be explored include:

- Age
- Sex
- Treatment
- MADRS Total Score
- SHAPS Score (0 – 14 scoring method)
- DARS Total Score

The parameter estimates, standard error, 95% confidence interval, degrees of freedom and p-values will be presented to for each model.

All data will be listed by treatment and patient.

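### No main PRT or EEfRT model adjusts for the patient's own baseline task result, although a pre-dose session is collected and FERT's second model does adjust

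*SAP*

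**What the plan says.** The task objective is secondary (SAP 2.2): "To evaluate the effects of BTRX-246040 on the performance of tasks as measured by the Facial Expression Recognition Task (FERT), Probabilistic Reward Task (PRT" and EEfRT). At Visit 2, before the first dose, "The rater will administer the Probabilistic Reward Task (PRT) and Effort Expenditure for Reward Task (EEfRT) in the order assigned by IWRS" (Protocol 9.2). The same instruction applies at Week 4, "The rater will administer the PRT and EEfRT in the order assigned by IWRS" (Protocol 9.5), and at Week 8 (Protocol 9.7). Protocol section 9 and a footnote to Table 1 ask sites, as far as possible, to hold these sessions at about the same time of day.

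The main models are:

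- **PRT (SAP 15.2.3.9).** "At each scheduled visit, an ANOVA model will be used to compare treatment groups". For the first two measures, "The models for response bias and discriminability will include terms for treatment, block, and treatment-by-block". Reaction time and hit rates add stimulus. Protocol 13.2.8.3 lists matching effects.
- **EEfRT completion (SAP 15.2.3.10).** "The analysis of completion rates will use an ANOVA model with a term for treatment", at each visit.
- **EEfRT preference (SAP 15.2.3.10).** A logistic GEE at each visit. "All models in the series will include explanatory variables reward magnitude, reward probability, and expected value", plus one variable of interest from age, sex, treatment, MADRS, SHAPS and DARS.
- **FERT, for comparison (SAP 15.2.3.8).** A first model has treatment only. A second has "additional factors of gender, baseline MADRS total score, and baseline FERT outcome measure".

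SAP 15.3.4 says that Week 8 change from baseline is to be analysed for each endpoint in its subgroup table, by the same method as the main analysis. The table marks PRT and EEfRT for the SHAPS ≤7 / >7 split.

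**The concern.** A pre-dose measurement of the outcome is usually the best single predictor of the on-treatment measurement, and here it is already in the database. Without it, stable differences between patients in reward learning and effort stay in the residual of the PRT and completion-rate ANOVAs, and a chance difference between arms at baseline carries into the Week 4 and Week 8 contrasts.

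The plan treats other endpoints differently. MADRS-6, the MADRS items, HADS, DARS and SHAPS are adjusted for their own baseline (SAP 15.2.3.2 to 15.2.3.6), and so are the exploratory HAM-A, pain and biomarker endpoints (SAP 15.3.3). PRT and EEfRT rank above those exploratory endpoints yet get a simpler model, and no reason is given.

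**Working it through.** **Model terms side by side**

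| Measure | Terms in the main model | Own-task baseline? |
|---|---|---|
| PRT response bias, discriminability | treatment, block, treatment × block | no |
| PRT reaction time, hit rates | the same plus stimulus | no |
| EEfRT completion rate | treatment | no |
| EEfRT preference (GEE) | three reward terms plus one variable of interest | no |
| FERT, second model | treatment, gender, baseline MADRS, baseline FERT measure | yes |

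**The plan's own figure.** Protocol 13.1 gives 44 per arm, effect size 0.5, two-sided alpha 0.10, two-sample t-test and 75% power, for MADRS. The noncentral t with 86 degrees of freedom and noncentrality 0.5 × √(44/2) = 2.35 gives 75.2%. The figure reproduces.

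**Illustration of the gain.** The documents state neither a task effect size nor a baseline-to-follow-up correlation ρ. I borrow the MADRS inputs, assume one normal value per patient, and vary ρ. Adjusting for baseline multiplies the residual variance by 1 − ρ², so the effect becomes 0.5/√(1 − ρ²), and the equivalent unadjusted sample is 44/(1 − ρ²).

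| ρ (assumed) | 1 − ρ² | Power | Equivalent n per arm |
|---|---|---|---|
| 0 | 1.00 | 75.2% | 44 |
| 0.1 | 0.99 | 75.6% | 44 |
| 0.2 | 0.96 | 76.7% | 46 |
| 0.3 | 0.91 | 78.6% | 48 |
| 0.5 | 0.75 | 85.1% | 59 |
| 0.6 | 0.64 | 89.7% | 69 |

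**Chance imbalance.** The standard error of the baseline difference is √(2/44) = 0.21 SD. At ρ = 0.5, a one-standard-error imbalance carries 0.5 × 0.21 ≈ 0.11 SD into the on-treatment contrast, about a fifth of a 0.5 SD effect.

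**Covariate or change score.** A raw change score has variance 2(1 − ρ) relative to the single value, which exceeds 1 when ρ < 0.5. At ρ = 0.3 its power is about 63% (normal approximation), against 75.8% unadjusted on the same approximation. It is not an equal substitute for the covariate.

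**Repeated rows in the PRT models.** SAP 15.2.1.9 has three blocks per session, and the block-level values are analysed. No patient term is stated. If blocks enter as independent rows, the true standard error of the treatment effect is about √(1 + 2 × ICC) times the reported one. For an assumed ICC of 0.3 to 0.5 that factor is 1.26 to 1.41, and a nominal 10% test rejects about 19% to 24% of the time under the null (18.8% and 24.9% in simulation). Adding the baseline mean alone does not cure this: in simulation, with the same ICCs and patient-effect correlations of 0.5 to 0.9, the test still rejected 15% to 23% of the time. The covariate and the patient-level term are both needed.

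**The case against.** An unadjusted comparison of randomized arms is unbiased, and in a correctly specified test chance imbalance is already covered by the error rate. These are nominal, multiplicity-unadjusted analyses in a Phase 2a trial that looks for trends (Protocol 13.2.1, SAP 7.4). Models run at every scheduled visit would display the arms at baseline, and Protocol 13.2.8 promises descriptive change-from-baseline summaries, so an imbalance would be visible. All of this stands. It makes the omission a matter of efficiency rather than an error, but displaying an imbalance does not adjust for it.

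Four stronger readings are tempting, and the documents do not support them:

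- *That no PRT or EEfRT analysis uses the baseline session.* SAP 15.3.4 calls, on its face, for change from baseline in both tasks within the SHAPS ≤7 / >7 subgroups. It also prescribes the main-analysis method, which has no change from baseline. The section is inconsistent and exploratory, and it does not repair the main models.
- *That these two tasks alone lack their own baseline.* The CGI-I responder model adjusts for baseline MADRS, not for a CGI baseline (SAP 15.2.3.7), and FERT's first model is treatment-only.
- *That the power figures describe the planned models.* They do not apply to the logistic GEE, which has no residual variance and whose odds ratio changes meaning when a covariate is added, or to the PRT model with several rows per patient. The validity checks in SAP 15.2.1.9 and 15.2.1.10 may also leave fewer than 44 usable patients per arm.
- *That the time-of-day instruction commits the plan to a within-patient comparison.* It applies only as far as possible, and no reason is given for it.

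**Conclusion.** The point holds for the main models: none of those serving the PRT and EEfRT part of the secondary objective uses the patient's own baseline result. The consequence is lost precision and uncorrected chance imbalance, not bias. Its size cannot be stated from the documents. It could be negligible (ρ of 0.2 or less) or worth about 10 points of power (ρ = 0.5) under the borrowed MADRS inputs and one normal value per patient.

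Two related matters rest on the text alone: SAP 15.3.4 does not match the main models, and the PRT models state no patient-level term despite repeated rows. The second can make reported standard errors too small if blocks are treated as independent. The SAP should be changed, because the data are already collected and the edit is small.

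**What to change.** 1. **PRT (SAP 15.2.3.9).** At Weeks 4 and 8, add the patient's baseline value of the same measure as a covariate (ANCOVA, not a raw change score). Include a patient random effect or a within-patient covariance for blocks and stimuli.
2. **EEfRT (SAP 15.2.3.10).** At Weeks 4 and 8, add baseline completion rate to the completion-rate model. Add the baseline proportion of hard-task choices to the treatment-series preference GEE only. It does not belong in the baseline-visit models, where it would be circular, and the age and sex series do not address the objective.
3. **Unusable baselines.** State a rule for sessions that are missing or fail the validity checks, for example substituting the overall baseline mean. Write it as an explicit covariate-only exception to the no-imputation statement in SAP 15.2.2.
4. **Supportive analysis.** Keep the model without the baseline covariate as supportive.
5. **Consistency.** Reconcile SAP 15.3.4 with the revised models, and update SAP 3.3, which declares no changes from the protocol.

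The cost is a small SAP edit and the handling rule; no new data are needed. Protocol 13.2.8.3 leaves the details of the task analyses to the SAP, and Protocol 13.2.1 requires an amendment only when a principal feature changes.
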